## 9. PATIENT REPORTED OUTCOME ANALYSES

### 9.1. Endpoint / Variables

Endpoint / Parameter/ Display Type	Absolute					
	Stats Analysis		Summary		Individual	
	T	F	T	F	F	L
Patient Reported Outcome						
SF-36 HR-QoL Scores (PCS, MCS, 8 subscales)			Y			Y
Changes from Baseline in SF-36 HR-QoL Scores (PCS, MCS, 8 subscales)	Y		Y			
EQ-5D-5L Scores			Y			Y
EQ-5D-5L Index Values			Y			Y
Changes from Baseline in EQ-5D-5L Index Value	Y		Y			
EQ VAS			Y			Y
Changes from Baseline in EQ VAS	Y		Y			

**NOTES :**

- T = Table, F = Figure, L = Listing, Y = Yes display generated.
- Stats Analysis = Represents TFL related to any formal statistical analyses (i.e. modelling) conducted.
- Summary = Represents TFL related to any summaries (i.e. descriptive statistics) of the observed raw data.
- Individual = Represents FL related to any displays of individual subject observed raw data.

**9.2. Summary Measure**

Scoring derivations are described in Section 15.6.7.

SF36 HR-QoL Scores and Changes from Baseline (PCS, MCS, 8 subscales)

The summary scores (PCS and MCS) and the domain scores (Physical Functioning [PF], Role-Physical [RP], Bodily Pain [BP], General Health [GH], Vitality [VT], Social Functioning [SF], Role-Emotional [RE], and Mental Health [MH]) will be summarized using mean, standard deviation, median, minimum, and maximum at each assessment visit by treatment group. For changes from baseline, the adjusted treatment difference and the 95% CIs will also be provided (See Section 15.6.7).

EQ-5D-5L / EQ VAS Scores and Changes from Baseline in EQ-5D-5L Index Value / EQ VAS

The number and percentage of subjects with each score within each category will be displayed at each assessment visit by treatment group. EQ-5D-5L index values and EQ VAS scores will be provided using mean, standard deviation, median, minimum, and maximum at each assessment visit by treatment group. For changes from baseline, the adjusted treatment difference and the 95% CIs will also be provided (See Section 15.6.7).

**9.3. Population of Interest**

The analyses will be based on the ITT population, unless otherwise specified.

**9.4. Strategy for Intercurrent (Post-Randomization) Events**

Any intercurrent events are taken to be irrelevant for the endpoints and the endpoints will be summarized based on available and observed data.

Analysis of change from baseline in the respective QoL parameter at each assessment visit will follow the strategy below.

Intercurrent events	Strategy
Study withdrawal / Intermittent missing	The following hypothetical scenario is considered to assess what would have happened if the event did not occur. Analysis using MMRM assume missing at random mechanism, that is the observations of missing depend on just observed values, not on unobserved values.

## 9.5. Statistical Analyses / Methods

Details of the planned displays are provided in [Appendix 10: List of Data Displays](#) and will be based on GSK data standards and statistical principles.

Unless otherwise specified, endpoints / variables defined in Section 7.3.1 will be summarized using descriptive statistics, graphically presented (where appropriate) and listed.

### 9.5.1. Statistical Methodology Specification

Endpoint / Variables

 
Change from baseline in the respective QoL parameter at each assessment visit
 

Model Specification

 
Analyses will be repeated for each QoL parameter (SF-36 HR-QoL scores/EQ-5D-5L index value/EQ-VAS score) using MMRM as specified in Section 7.4.5.1:
 
Note that the QoL parameters are no need to be log-transformed as opposed to some of the iron parameters.
 

Model Results Presentation

 
The adjusted mean change from baseline will be presented with the associated 95% CIs by treatment at each assessment visit. The adjusted treatment difference (daprodustat – darbepoetin alfa) for change from baseline will also be presented with the associated 95% CI at each assessment visit.
 

Subgroup Analyses

 
Not applicable
 

## 10. PHARMACOKINETIC ANALYSES

### 10.1. Pharmacokinetic Analyses

#### 10.1.1. Endpoint / Variables

The details of the planned displays are presented in [Appendix 10: List of Data Displays](#).

Endpoints	Untransformed				Log-Transformed			
	Summary		Individual		Summary		Individual	
	F	T	F	L	F	T	F	L
Plasma Concentrations of Daprodustat	Y 	Y	Y 	Y				
Derived PK Parameters	Y 	Y 	Y 	Y		Y 		
Dose Normalized PK Parameters	Y 	Y 	Y 	Y		Y 		

#### NOTES :

- T = Table, F = Figures, L = Listings, Y = Yes display generated.
  - Summary = Represents TFL related to any summaries (descriptive statistics) of the observed raw data.
  - Individual = Represents FL related to any displays of individual subject observed raw data.
1. Linear and Semi-Log plots will be created on the same display.
  2. Separate Mean ( $\pm$  SD) and Median plots will be generated.
  3. Individual PK parameters calculated based on less than 4-time point concentrations or any time deviated concentration will be omitted from summaries and figures.

#### 10.1.1.1. Drug Concentration Measures

Refer to [Appendix 5: Data Display Standards & Handling Conventions \(Section 15.5.3 Reporting Standards for Pharmacokinetic\)](#)

Concentrations of daprodustat in plasma will be listed and summarized by dose group and nominal time. Individual plasma concentration-time profiles and median/mean profiles by dose group will be plotted. Each of figures will contain one plot on the untransformed scale (i.e. a linear plot) and one plot on the log transformed scale (i.e. a log-linear plot).

#### 10.1.1.2. Derived Pharmacokinetic Parameters

Derivation of pharmacokinetic parameters will be performed by, or under the direct auspices of, Clinical Pharmacology & Science Promotion Office, GlaxoSmithKline K.K.

Pharmacokinetic parameters will be calculated by standard non-compartmental analysis according to current working practices and using the currently supported version of WinNonlin (version 6.3 or higher). All calculations of non-compartmental parameters will be based on actual sampling times. Pharmacokinetic parameters listed will be determined from the plasma daprodustat concentration-time data, as data permits.

Parameter	Parameter Description
AUC(0-4)	Area under the concentration-time curve from time zero to the time of the last quantifiable concentration (C(last)) will be calculated using the linear trapezoidal rule for each incremental trapezoid and the linear trapezoidal for each decremental trapezoid. The concentration at 0 hr will be set to 0.
Cmax	Maximum observed concentration, determined directly from the concentration-time data.
Tmax	Time to first occurrence of Cmax will be obtained directly from the concentration-time data.

**NOTES:**

- Additional parameters may be included as required.
- C(last) is expected to be the concentration observed at 4 hours after the most recent dose.

**10.1.2. Summary Measure**

Refer to Section [15.5.3](#) for the display standards.

- ***Plasma Daprodustat Concentrations***

Non-transformed and log-transformed plasma concentration at every scheduled time point will be summarized at Week 12, Week 24, and all visits (i.e., pooled analysis of Week 12 and Week 24) by dose level. Non-transformed plasma concentration of daprodustat will be summarized using mean, 95% CI, standard deviation, median, minimum, and maximum. Log-transformed plasma concentration of daprodustat will be summarized using geometric mean, 95% CI of geometric mean, standard deviation of log-transformed data and between subject coefficient of variation (%CVb).

- ***PK Parameters***

Non-transformed and log-transformed PK parameters will be summarized at Week 12, Week 24, and all visits (i.e., pooled analysis of Week 12 and Week 24) by dose level. Non-transformed PK parameters of daprodustat (AUC(0-4), Cmax, and Tmax) will be summarized using mean, 95% CI, standard deviation, median, minimum, and maximum. Log-transformed PK parameters of daprodustat (AUC(0-4), Cmax, and Tmax) will be summarized using geometric mean, 95% CI of geometric mean, standard deviation of log-transformed data and between subject coefficient of variation (%CVb).

Dose normalized PK parameters (non-transformed and log-transformed) will also be summarized in the same manner by dose level. In summary of dose normalized PK parameters, summary tables by tablet strength (non-transformed and log-transformed) will be provided.

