- 12. For re-screening subjects, no repeated ophthalmology exams could be required at re-screening, in which case the results of ophthalmology exams at the most recent screening could be replaced on the investigator's (or subinvestigator's) discretion if re-screening subjects meet all of the following criteria:
 - There were no findings that would suggest a repeat ophthalmology exam performed within the next 3 months at the latest screening ophthalmology exam.
 - No new ocular symptoms or complaints were noted after the most recent ophthalmologic screening and before the next re-screening.
 - The most recent ophthalmology screening was performed within 3 months prior to anticipated Day 1.
- 13. Only SAEs assessed as related to study participation or a GSK product are collected.
- 14. For withdrawn subjects, specified assessments should be done wherever possible.

Table 11 Blood Sampling Schedule for Pharmacokinetics

PK sample	Week 12 ²	Week 24 ²	
Blood sampling timing 1	1, 2, 3, and 4 h after administration of daprodustat or placebo		

Subjects must take the study medication with regard to blood sampling time. Subjects will record the date and time of the last two study medication doses taken prior to blood sampling in the medication diary. There should be an interval of at least 12h (preferably, almost 24 h) between these two doses.

- 1. Blood sampling should be completed within +/- 30 min of the planned collected time.
- 2. Blood sampling not performed at this visit may be postponed until the following visits.

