### 15.3. Appendix 3: Assessment Windows

All data will be reported according to the nominal visit date for which it was reported (that is, no visit windows will be applied during dataset creation). Permissible range at each visit was specified in time & event table (See [Appendix 2](#)). Records in the eCRF unscheduled visit will not be slotted to a particular time point, but remain as unscheduled if they are either summarized or listed unless otherwise specified.

Regarding the visits where only HemoCue Hgb is available (i.e., Week 2, Week 6, Week 10, etc. See [Appendix 2](#)), the Hgb values will not be used for any analyses but presented in the listing unless otherwise specified.

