### 15.5.3. Reporting Standards for Pharmacokinetic

Pharmacokinetic Concentration Data	
PC Windows Non-Linear (WNL) File	PC WNL file (CSV format) for the non-compartmental analysis by Clinical Pharmacology Modelling and Simulation function will be created according to GUI_51487. Note: Concentration values will be imputed as per GUI_51487
Descriptive Summary Statistics, Graphical Displays and Listings	Refer to IDSL PK Display Standards. Refer to IDSL Statistical Principle 6.06.1. Note: Concentration values will be imputed as per GUI_51487 for descriptive summary statistics/analysis and summarized graphical displays only.
Pharmacokinetic Parameter Derivation	
PK Parameter to be Derived by Programmer	The following PK parameters will be derived by the Programmer: 
 
Dose-Normalized PK parameters
 

Pharmacokinetic Parameter Data	
Is NQ impacted PK Parameters Rule Being Followed	Yes, refer to Standards for Handling NQ Impacted PK Parameters.
Descriptive Summary Statistics, Graphical Displays and Listings	Each pharmacokinetic parameter (AUC(0-4), C max , and T max ) will be summarized using the minimum set of summary statistics (IDSL statistical display principle 6.06.1). For each pharmacokinetic parameter (AUC(0-4), C max , and T max ), the log-transformed parameter will be summarized using the summary statistics. The summary statistics are: N, n, geometric mean, 95% CI of geometric mean, standard deviation (SD) of log-transformed data and between subject coefficient of variation (CV b (%)) will be reported. [1] $CV_b (\%) = \sqrt{(\exp(SD^2) - 1) * 100}$ (SD = SD of log transformed data)

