### 15.6.5. Pharmacokinetic

General
Dose Level

 
Summaries by dose level and used tablet strength will be based on an actual dose associated with a container number. (See Section 15.6.2). Tablet strength is defined as follows: 
 
Actual dose = 1 mg → 1 mg tablet strength
 
Actual dose = 2 mg → 2 mg tablet strength
 
Actual dose = 4 mg → 4 mg tablet strength
 
Actual dose = 6 mg → 6 mg tablet strength
 
Actual dose = 8 mg → 4 mg tablet strength
 
Actual dose = 12 mg → 6 mg tablet strength
 
Actual dose = 18 mg → 6 mg tablet strength
 
Actual dose = 24 mg → 6 mg tablet strength
 
 
 
Dose level which is actually provided to subjects will be derived from an actual dose of the visit (including unscheduled visit) which meets the following: 
 
Treatment Start Date ≤ Date of last dose taken prior to PK sampling ≤ Treatment Stop Date
 
 
 

Others

 
Dose normalized PK parameters will be derived from [PK parameters / actual dose (mg)].
 
In aggregated analyses, data collected in Week 12 and Week 24 will be aggregated.
 
For the PK parameters calculation, the concentration at 0 hr will be set to 0 and assign zero to NQ values.
 
Individual's PK parameters calculated less than 4-time point concentrations or any time deviated (beyond ± 30 min of scheduled timepoints) concentrations will be omitted from summaries and figures, but presented in a listing.
 

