## 15.10.4.8. Pharmacokinetic Figures

Pharmacokinetic Figures					
No.	Population	IDSL / TST ID / Example Shell	Title	Programming Notes	SAC
Plasma Daprodustat Concentrations					
5.1.	PK	PK24	Individual Daprodustat Plasma Concentration-Time Plots	(Linear and Semi-Log) (by Dose)	Y
5.2.	PK	PK17	Mean Daprodustat Plasma Concentration-Time Plots	(Linear and Semi-Log) (by Dose)	Y
5.3.	PK	PK19	Mean (+SD) Daprodustat Plasma Concentration-Time Plots	(Linear and Semi-Log) (by Dose)	Y
5.4.	PK	PK20	Median Daprodustat Plasma Concentration-Time Plots	(Linear and Semi-Log) (by Dose)	Y
PK parameters					
5.5.	PK	PK_F1	Individual Plot of Daprodustat Dose Level and PK Parameters (AUC(0-4) and Cmax)	will provide only pooled data	Y
5.6.	PK	PK_F2	Mean (+SD) Plot of Daprodustat Dose Level and PK Parameters (AUC(0-4) and Cmax)	will provide only pooled data	Y
5.7.	PK	PK_F3	Median Plot of Daprodustat Dose Level and PK Parameters (AUC(0-4) and Cmax)	will provide only pooled data	Y
5.8.	PK	PK_F1	Individual Plot of Daprodustat Dose Level and Dose Normalized PK Parameters (AUC(0-4) and Cmax)	will provide only pooled data	Y
5.9.	PK	PK_F2	Mean (+SD) Plot of Daprodustat Dose Level and Dose Normalized PK Parameters (AUC(0-4) and Cmax)	will provide only pooled data	Y
5.10.	PK	PK_F3	Median Plot of Daprodustat Dose Level and Dose Normalized PK Parameters (AUC(0-4) and Cmax)	will provide only pooled data	Y
5.11.	PK	PK_F4	Box Plot of Daprodustat Dose Level and Dose Normalized PK Parameters (AUC(0-4) and Cmax)	will provide only pooled data	Y
5.12.	PK	PK_F1	Individual Plot of Daprodustat Used Tablet Strength and Dose Normalized PK Parameters (AUC(0-4) and Cmax)	will provide only pooled data	Y
5.13.	PK	PK_F2	Mean (+SD) Plot of Daprodustat Used Tablet Strength and Dose	will provide only pooled data	Y

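### The pooled Week 12 and Week 24 PK tables have no step for subjects who contribute two profiles to the same row, so their 95% CIs are too narrow where that happens

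*SAP*

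**What the plan says.** Protocol Table 11 schedules PK sampling at Week 12 and Week 24. SAP 10.1.2 plans summaries of concentrations, AUC(0-4), Cmax and Tmax at each visit and also for "all visits (i.e., pooled analysis of Week 12 and Week 24) by dose level". SAP 15.6.5 describes the pooling in one sentence: "In aggregated analyses, data collected in Week 12 and Week 24 will be aggregated".

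The statistics are the ordinary descriptive set. For log-transformed parameters SAP 15.5.3 lists "N, n, geometric mean, 95% CI of geometric mean, standard deviation (SD) of log-transformed data" and a between-subject CV computed as sqrt(exp(SD²) − 1) × 100 from that same SD. For dose-normalised parameters, "summary tables by tablet strength (non-transformed and log-transformed) will be provided" in addition to the tables by dose level. The programming note for PK parameter Figures 5.5 to 5.15 in SAP 15.10.4.8 is "will provide only pooled data".

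On missed sampling, note 2 to Protocol Table 11 says: "Blood sampling not performed at this visit may be postponed until the following visits". SAP Appendix 3 says: "All data will be reported according to the nominal visit date for which it was reported". It applies no visit windows and leaves unscheduled records unslotted.

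**The concern.** A pooled row can hold two profiles from one person. A standard CI on the aggregated records treats them as two people. Log exposure in the same subject on the same dose 12 weeks apart would usually be positively correlated, so the second profile adds less information than a new subject would, and the interval claims too much precision.

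The SAP specifies repeated-measures models where it wants them: for Hgb (7.1.5.1), iron parameters (7.4.5.1) and QoL (9.5.1). For the pooled PK tables it gives no within-subject averaging, no one-record-per-subject rule and no subject effect. AUC and Cmax are a stated secondary endpoint, so at stake are the error bars reported for exposure at each dose and tablet strength. It is also unclear whether n in a pooled row counts subjects or profiles.

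**Working it through.** **Plan's own figure.** The documents state no PK sample size, CV or CI width, so there is nothing to reproduce.

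**Inputs from the documents.** Two PK visits; grouping by dose level or tablet strength; at most 135 daprodustat subjects (Protocol 4.3) over 8 dose levels, or 135/8 ≈ 17 per level on average. Doses can change every 4 weeks (Protocol 6.4.1.2), so there are (24 − 12)/4 = 3 dose decisions between the two profiles.

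**Assumptions, not in the documents.** Within-subject correlation ρ of the log values, 0 to 0.9; share f of subjects in a row who have both profiles in it, 0 to 1.

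**Who repeats.** In a dose-level row, only subjects on the same dose at both visits. By tablet strength, SAP 15.6.5 maps doses 1, 2, 4, 6, 8, 12, 18, 24 mg to strengths 1, 2, 4, 6, 4, 6, 6, 6 mg. Of the seven one-step dose changes, five (1–2, 2–4, 4–6, 6–8, 8–12) also change strength and two (12–18, 18–24) do not. Overlap by strength is therefore at least that by dose level, but need not be near complete.

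**Formula.** With n subjects, n(1+f) records and log-scale variance σ²:

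- variance the ordinary CI assumes: σ² / [n(1+f)]
- true variance: σ² [(1−f) + 2f(1+ρ)] / [n(1+f)²]
- width ratio = √(assumed/true) = √[(1+f) / (1+f+2fρ)], which is 1/√(1+ρ) when f = 1

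Example, f = 0.5 and ρ = 0.5: √(1.5/2.0) = 0.87.

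| | ρ = 0 | 0.3 | 0.5 | 0.7 | 0.9 |
|---|---|---|---|---|---|
| Width ratio, f = 1 | 1.00 | 0.88 | 0.82 | 0.77 | 0.73 |
| Width ratio, f = 0.5 | 1.00 | 0.91 | 0.87 | 0.83 | 0.79 |
| Width ratio, f = 0.25 | 1.00 | 0.95 | 0.91 | 0.88 | 0.86 |
| Width ratio, f = 0 | 1.00 | 1.00 | 1.00 | 1.00 | 1.00 |
| Coverage, f = 1 | 95% | 91.5% | 88.9% | 86.2% | 83.4% |
| Coverage, about half repeating | 95% | 92.7% | 90.9% | 89.0% | 86.9% |

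Coverage is simulated: 40,000 runs per setting, 15 subjects in a row (8 of 15 repeating in the last line), t-interval on all records. Results for 8 and 30 subjects are similar. A t-interval on one mean log value per subject kept 95% coverage throughout.

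**%CVb.** With f = 1 the expected pooled variance is σ²(2n − 1 − ρ)/(2n − 1). For n = 15 and ρ = 0.9 that is 28.1/29 = 0.97 of σ². Pooling hardly changes the size of the CV; it does give double weight to subjects with two profiles.

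**The case against.** - **The SAP does not say that the records are independent.** True. It says only that data are aggregated, and refers display details to company PK standards and separate mock shells. Independence is inferred from an ordinary CI applied to aggregated data. It is the natural reading, and nothing in the SAP text points to another.
- **Not all subjects count twice.** This stands. A reader might infer that every subject is doubled, or nearly every one in the tablet-strength tables because the 6 mg tablet serves four doses. The dose rules and the tablet map do not support either. SAP 15.6.5 also drops PK parameters based on fewer than four time points or on time-deviated samples, which can reduce the overlap.
- **The pooled tables are not the only result.** This stands. Week 12 and Week 24 are also summarised separately. The pooled-only figures are individual, mean (+SD), median and box plots, and none is described as showing a CI. No PK hypothesis is tested, and dosing follows HemoCue Hgb.
- **The %CVb mixes within- and between-subject variation whether or not visits are pooled.** This stands. A single-visit SD contains both, so the label is not a fault of pooling.
- **Postponed profiles are not shown to be lost.** This stands. A reader might infer that a profile drawn later falls outside both visits. That follows only if it is entered under the later visit or as unscheduled; reported for Week 12, it stays in Week 12. SAP 15.6.5 takes the dose level of a PK sample from visits including unscheduled ones, so such samples were foreseen. What is missing is a rule assigning them to a PK occasion.

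**Conclusion.** The point holds within limits. Followed as written, the pooled tables give a 95% CI of the geometric mean that is too narrow in any row where subjects appear twice and ρ is positive. Relative to a CI with the correct variance, the loss of width for ρ of 0.3 to 0.9 is 12% to 27% if all subjects repeat and 9% to 21% if half do. It is nil if none repeat or if ρ is 0. Both quantities are assumptions, so the size in this trial cannot be fixed in advance. The effect is confined to descriptive pooled tables of a secondary endpoint. The handling of postponed profiles is a missing detail, not a demonstrated loss of data.

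**What to change.** In SAP 10.1.2 and 15.6.5, state that for pooled summaries the log-transformed value is first averaged within subject and dose level (within subject and tablet strength for the dose-normalised tables by strength). For concentrations, do this at each nominal time. Then compute the geometric mean, 95% CI and %CV over subjects, and report numbers of subjects and profiles separately. Label the %CV as based on subject averages, because averaging two profiles reduces the within-subject part.

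A random-subject model is an alternative. It is not identical when some subjects have one profile and others two, because the weights differ; the SAP should name one method.

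As a clarification only, say to which PK occasion a profile postponed under Table 11 note 2 belongs.

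The cost is SAP wording and a few lines of code; no new data are needed. The CIs widen. In the 15-subject simulation with ρ of 0.3 to 0.9, the ordinary pooled interval averaged 0.84 to 0.68 of the subject-average interval when all repeated, and 0.87 to 0.78 when about half did. A small part of that is the price of the simpler method rather than correction: at ρ = 0 the ratios were already 0.96 and 0.92.

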**10.1.3. Population of Interest**

The pharmacokinetic analyses will be based on the PK population, unless otherwise specified.

#### **10.1.4. Strategy for Intercurrent (Post-Randomization) Events**

Any intercurrent events are taken to be irrelevant for pharmacokinetic endpoints. The pharmacokinetic endpoints will be summarized based on available and observed data.

**11. POPULATION PHARMACOKINETIC (POPPK) ANALYSES**

No population pharmacokinetics analyses are planned for this study, but the pharmacokinetic data may be used for a separate report.

